1. ABSTRACT

The impact of pelvic joint stiffness on the fear of falling in subjects over 75 years of age, hospitalized or in an institution. Study of a cohort of 100 patients.

JS (joint stiffness associated with fear of falling)

Background:

Purpose:

Fear of falling is one of the most concern in geriatric medicine. It could modify the daily activities of the elderly and create secondary troubles like sarcopenia, depression, it decreases the quality of life for this population.

Abstract: Fear of falling is defined as the enduring preoccupation with falling, leading the person to avoid activities that they are capable of doing. It modifies its behavior and affects its quality of life, its well-being and increases the risk of developing pathologies linked to the lack of physical activities. Joint stiffness is a major disorder in the elderly linked to bone and joint aging, but also to lack of mobilization. The pelvic girdle is the mechanical structure at the center of the balance and gait systems. The lack of amplitude of the joints that compose it could induce a fear of falling.

This study seeks to highlight whether there is an association between the fear of falling and the lack of amplitude of the different joints of the pelvic girdle.

Primary outcome:

Highlight a significant positive association between the Schober index (quantitative) and / or hip flexion goniometry (quantitative) and / or hip extension goniometry (quantitative) with the FES-I score (qualitative 2 groups).

Secondary outcomes: - Validity of 3 FES-I categories according to anthropometric measurements

- Evaluation of the linearity of the association
- Assessment of the strength of association
- Impact of cofactors collected on FES-I (polypharmacy, history of fall)

Study design: description of the main features of the research according to type of research

Eligibility criteria:

inclusion criteria:

- over 75 years old
- Ability to understand and answer a questionnaire in French
- Ability to stand up
- Patient from the Melun hospital (santé pole center+ nursing home of the GHSIF)
- Affiliated with a social security scheme

exclusion criteria:

- mental disorders, lumbar surgery

Interventions: Procedure: Study of a cohort of 100 patients

1 / evaluation of the fear of falling using an FES-I questionnaire, distribution of subjects according to the score into 3 groups (16-19: little concerned by the fear of falling, 20-27 moderately concerned, 28-64 very concerned by fear of falling)

2 / evaluation of lumbar articular mobility by the schober index, coxofemoral by hip goniometry in flexion and extension (no evaluation of other amplitudes because lack of abduction / abduction / external and internal rotation of the hip remain functional in walking and the balance)

Number of subjects: 100

Statistical analysis: Pearson and Mann Whitney Correlation Test Chi-2 Test

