2.1.3. DESCRIPTION AND RATIONALE OF THE STUDY POPULATION

The aim of this study is to determine whether the intensity of joint stiffness is associated with high apprehension of falling in elderly patients.

We chose to carry out the study in this population because: hospitalized patients or residents of Residential Care Facility for Dependent Elderly People (EHPAD in French) are at greater risk of fear of falling.

2.1.4. JUSTIFICATION FOR THE DURATION OF THE STUDY.

A retrospective analysis of observational data carried out on a sample drawn from a similar population enabled us to calculate the minimum number of subjects required to demonstrate a statistically significant association between the reference test and at least one of the variables studied. It is worth noting that 100 patients are required to reject the null hypothesis of the primary objective with 90% power and 5% risk. Given the number of geriatric patients at the Southern Ile-de-France Hospital Group (GHSIF), a 6-month period is planned to reach the number of patients required for this study.

Once a patient is included in the study, the total duration of his/her participation is 30 minutes. Inclusion and evaluation of patients is carried out progressively over the course of the study.

The total duration of the study is therefore estimated at 6 months.

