4. EVALUATION CRITERIA

4.1. MAIN EVALUATION CRITERION

FES-I questionnaire

This questionnaire comprises sixteen items. It is an improved version of the Fall Efficacy Scale (FES) proposed by Tinetti (18). The FES-I was developed by the Prevention of Falls Network Europe (ProFaNE). It is available on the ProFaNE website. A version of the FES-I scale has been translated into French. The questionnaire works as follows: for each proposition (16 in all), respondents are asked to rate their level of anxiety when imagining themselves carrying out the corresponding action. For each item, the respondent's level of concern is rated on a scale from 1 to 4, with the following correspondences:

- 1 not at all worried;
- 2 a little worried;
- 3 quite worried;
- 4 very worried.

The final score for this test is therefore between 16 and 64. The higher the score, the greater the fear of falling. The cut-point for this questionnaire, defining a high level of apprehension about falling, is set for scores greater than or equal to 28, according to research by (Delbaere et al, 2010)⁵

Hip goniometry

Hip goniometry: expressed in degrees, measures hip joint amplitude in active flexion and extension using a goniometer. The measurement is taken standing up. We evaluate one hip, the one that appears most mobile to the patient. With the goniometer at the level of the greater trochanter, we ask the patient to actively flex the hip, knee bent, checking that the lumbar vertebrae are not engaged. Same procedure on the same leg for straight-leg hip extension.

Modified Schober index

Modified Schober Index: This test is used to identify patients with ankylosing spondylitis (Macrae & Wright, 1969)⁶ and assesses lumbar joint mobility in flexion. Subsequent studies have shown the test to be reliable and reproducible (Koppenhaver *et al.*, 2011)⁷, (Malanga *et al.*, 2005)⁸.

- When the patient is standing, a first mark is made at the sacro-lumbar junction or between the posterior-superior iliac spines;
- a second mark is made 10 cm above the sacro-lumbar junction;
- a third mark is made 5 cm below the sacro-lumbar junction;
- a measuring tape is stretched between the three marks and the distance between the first and third marks is recorded, in neutral position and at maximum flexion of the lumbar spine;
- a deviation of less than 5 cm is considered pathological.

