12. QUALITY CONTROL AND ASSURANCE

12.1. DATA COLLECTION INSTRUCTIONS

All information required by the protocol must be recorded in the observation notebooks, and any missing data must be explained. Data should be collected as they are obtained, and transcribed neatly and legibly into the notebooks.

Erroneous data recorded in the observation notebooks should be clearly crossed out, and the new data should be copied next to the crossed-out information, accompanied by initials, date and, where appropriate, a justification by the person directing and supervising the research, or the authorized person who made the correction.

For the purposes of this study, data will be collected on a paper observation notebook.

Data collection will be carried out by: the investigator at each site

Data will be collected during the patient's stay and hospitalization.

The data collected in this study will be:

- Age
- gender
- History of falls
- Number of current drug treatments
- FES-I questionnaire score
- Hip goniometry in flexion
- Hip goniometry in extension
- Lumbar schober index

The data used in this study will come from: patients' medical records, the FES-I questionnaire and the measurements taken.

In order to carry out this study, pseudonymized data will be transmitted to the promotion unit of the clinical research unit

12.2. IDENTIFICATION OF DATA COLLECTED DIRECTLY IN THE CASE REPORT FORMS, WHICH WILL BE CONSIDERED AS SOURCE DATA

The observation book data used as source data are:

- FES-I score
- Schober index
- Hip goniometry in flexion
- Hip goniometry in extension

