12.3. DATA CIRCUIT

For each patient, data from the medical record and consultation (clinical examination and questionnaire) are collated in the observation notebook.

Data from the observation book is pseudonymized and entered into the database. The database is frozen and the data analyzed statistically.

The results of this study will first be presented in a thesis/internship report.

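### Nothing in the plan keeps the examiner unaware of FES-I when mobility is measured, so the three primary readings could drift toward the hypothesis; a short rule in 8.4 would reduce this

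*Combined protocol and SAP*

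**What the plan says.** - **Order.** The procedure in the abstract (section 1) has two numbered steps. The first is "evaluation of the fear of falling using an FES-I questionnaire, distribution of subjects according to the score into 3 groups". The second is "evaluation of lumbar articular mobility by the schober index, coxofemoral by hip goniometry in flexion and extension". The table of research phases in 8.2 also lists the questionnaire above the clinical examination. Section 8.4, which describes the visit, sets no order.
- **Who measures.** Section 12.1 states: "Data collection will be carried out by: the investigator at each site".
- **Setting.** There is a single contact. Section 2.1.4 says: "Once a patient is included in the study, the total duration of his/her participation is 30 minutes".
- **Records.** Under 12.3, "data from the medical record and consultation (clinical examination and questionnaire) are collated in the observation notebook". Section 12.2 lists the FES-I score, with the three mobility values, among the data for which the notebook is itself the source.
- **How mobility is read.** For hip flexion (4.1), "we ask the patient to actively flex the hip, knee bent, checking that the lumbar vertebrae are not engaged". For the Schober index, the first mark may be placed at either of two landmarks, and the second reading is taken at the patient's furthest flexion.
- **Use.** Section 9 compares the three measures between group A (FES-I below 28) and group B (28 to 64) by Mann-Whitney tests.

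The text mentions no masked or separate examiner, no sealed questionnaire, and no rule on when the score is totalled.

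**The concern.** FES-I defines the groups, and mobility is what is compared between them. An examiner who has just heard or seen sixteen answers has a good idea of which group the patient will fall into, even without adding them up. That examiner then chooses the landmark, encourages an active movement, decides when it has ended and judges whether the lumbar spine has moved. The investigator also knows the hypothesis in 2.2, that stiffer joints go with more fear. Slightly lower readings in fearful patients are therefore the plausible direction of error.

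Such error differs between groups. A larger sample does not dilute it, and the correlation, regression and subgroup analyses in section 9 use the same readings, so they would carry it too. It could produce an association where none exists, or enlarge a real one, on all three primary measures.

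**Working it through.** **The plan's own figure.** Section 2.1.4 gives 100 patients for 90% power at 5% risk. It gives no effect size, SD, A:B split or sidedness, so the figure cannot be derived forward. Solving backwards with an assumed 50/50 split and a two-sided test:

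- two means: d = (1.960 + 1.282) / √(50 × 50 / 100) = 3.242 / 5 = 0.648
- Mann-Whitney (efficiency 3/π = 0.955): d = 3.242 / √(25 × 0.955) = 0.663

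So 100 patients fits a difference of about two thirds of an SD. The question is how a smaller artificial difference would behave.

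**Illustration.** Assume no true association, and readings in group B lowered by δ SD through examiner drift. The chance that one two-sided Mann-Whitney test gives p < 0.05 is approximately

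Φ(a − 1.960) + Φ(−a − 1.960), with a = δ × √(n₁n₂/N × 3/π).

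With 50/50, a = 4.886 δ. For δ = 0.2, a = 0.977, and Φ(−0.983) + Φ(−2.937) = 0.163 + 0.002 = 0.165.

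| Assumed drift δ (SD) | Formula, 50/50 | Simulation, 3,000 runs, 50/50 | Simulation, 10,000 runs, 50/50 | Formula, 30/70 |
|---|---|---|---|---|
| 0 | 0.050 | 0.053 | 0.047 | 0.050 |
| 0.1 | 0.078 | 0.078 | 0.077 | 0.073 |
| 0.2 | 0.165 | 0.166 | 0.159 | 0.146 |
| 0.3 | 0.311 | 0.301 | 0.292 | 0.269 |

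Formula and simulations agree to within about two percentage points: about 8%, 17% and 30% with equal groups, and somewhat less with a 30/70 split. The drift sizes and the splits are assumptions. The documents give no SD for the three measures, so the drift cannot be expressed in degrees or centimetres.

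**What the remedy does to these numbers.** It changes neither the sample size nor the power. If drift were zero, each test would return to its nominal 5%.

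**The case against.** - **The sequence is inferred.** No section says that the investigator totals FES-I or assigns a group before measuring. The order comes from a numbered list in the abstract, which may only name the study's components, and from row order in a table. The three categories in that list are not the two-group split of the primary test, which section 9 describes as an analysis step; 14.1 gives the analysis to the unit's biostatistician. A reader might infer that the same person scores and groups each patient and then measures. That is possible, but it is not stated. Section 8 also announces a process diagram that is absent from the text reviewed; if it fixes an order, it should be read first. What stands is that the written plan permits this sequence and nothing in it prevents it.
- **A single assessor is not stated either.** Section 12.1 assigns responsibility by site, while 8.4 and 12.5 allow for other qualified people. This stands, but no section requires the two tasks to be separated.
- **The Schober index is partly standardised.** The second and third marks lie at fixed distances from the first, and "a measuring tape is stretched between the three marks". This limits judgement, but leaves the choice of first landmark and the end of flexion. The lumbar check in goniometry is the clearer case.
- **The size is invented.** This is correct. The reliability coefficients in 4.1 describe scatter, not direction, and cannot supply a drift size. A reader might also quote the chance that at least one of the three measures is significant. That figure is already 1 − 0.95³ = 14% with no drift if the tests are independent, so it mixes in a separate multiplicity question and is not used here.
- **A reader might infer that measuring mobility first removes the problem at no cost.** The documents do not support this. Fall history is collected (12.1) and hesitancy is visible, so the examiner may still guess. In FES-I, "respondents are asked to rate their level of anxiety when imagining themselves carrying out the corresponding action", so a hard standing test just beforehand could colour the answers. An investigator who reads the items aloud knowing the mobility values could bias FES-I instead.

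**Conclusion.** The concern holds as a gap in the plan, not as a shown bias. FES-I is listed before mobility, the site investigator collects the data, the readings involve judgement, and the text has no provision to keep the examiner unaware of FES-I. Drift toward the hypothesis is therefore possible, and the planned analyses could not correct it.

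Its size is unknown. If drift reached 0.1, 0.2 or 0.3 SD, one test under no true association would be significant in about 8%, 17% or 30% of studies instead of 5%. This rests on the assumed drift, on 50/50 groups, and on normally distributed readings with equal spread. It is a worthwhile and inexpensive correction, not a fatal flaw.

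**What to change.** Add to 8.4:

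1. Where the patient can, FES-I is self-completed and stays closed and unscored until the three mobility values are written in the notebook.
2. The notebook records whether help was needed and the order used.
3. Once the mobility values are written, and before the patient leaves, the form is checked for blank items without totalling the score.
4. Groups A and B are formed from the database at analysis, as section 9 already implies.
5. If the items must be read aloud, one order is fixed for all such patients and recorded, and the report states the remaining risk of bias.

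**Cost.** A few sentences, with no change to the sample size or the tests and no added staff. There are two small downsides. Self-completed forms may be left incomplete: eligibility (6.1) asks that patients can understand and answer a questionnaire, not that they complete it unaided, and an incomplete FES-I is a stopping rule in 8.8. Item 3 addresses this. Where mobility is taken first, some carry-over to FES-I is possible. The change reduces examiner bias; it cannot hide fall history or visible hesitancy, and the report should say so.

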2. SCIENTIFIC JUSTIFICATION

2.1. CURRENT STATE OF KNOWLEDGE

2.1.1. PATHOLOGY

Fear of falling is defined as the enduring preoccupation with falling, leading the person to avoid activities he/she is capable of performing. (Tinetti & Powell, 1993)¹. Anxiety linked to the fear of falling can have a significant impact on a person's activities and independence, and can lead to the deconditioning of their functional capacities. The subject feels his or her fragility and dependence on others, and becomes aware of his or her ageing.

2.1.2. REFERENCE STRATEGIES/PROCEDURES

The risk factors for fear of falling are essentially psychological, age-related and social. Management of the fear of falling responds to the origin of the problem, but remains multidimensional and multidisciplinary. The aim is to reassure the sufferer, while encouraging him or her to participate as fully as possible in everyday activities. By combining behavioral and cognitive therapies with physiotherapy, we can improve the symptomatology and prognosis of elderly sufferers.

The physical component is not well identified as a risk factor in elderly people afraid of falling. However, studies have shown that physical exercise based on gentle muscle strengthening and proprioception, such as Tai Chi, helps to reduce the fear of falling in the short term (Kendrick & al, 2014)⁽²⁾ (Taggart, 2002)³. Fessel and Nevitt also found that fear of falling motivated many elderly people with Rheumatoid Arthritis (RA) to avoid or modify specific activities (Fessel & Newitt, 2005)⁴.

2.1.3. DESCRIPTION AND RATIONALE OF THE STUDY POPULATION

The aim of this study is to determine whether the intensity of joint stiffness is associated with high apprehension of falling in elderly patients.

We chose to carry out the study in this population because: hospitalized patients or residents of Residential Care Facility for Dependent Elderly People (EHPAD in French) are at greater risk of fear of falling.

2.1.4. JUSTIFICATION FOR THE DURATION OF THE STUDY.

A retrospective analysis of observational data carried out on a sample drawn from a similar population enabled us to calculate the minimum number of subjects required to demonstrate a statistically significant association between the reference test and at least one of the variables studied. It is worth noting that 100 patients are required to reject the null hypothesis of the primary objective with 90% power and 5% risk. Given the number of geriatric patients at the Southern Ile-de-France Hospital Group (GHSIF), a 6-month period is planned to reach the number of patients required for this study.

Once a patient is included in the study, the total duration of his/her participation is 30 minutes. Inclusion and evaluation of patients is carried out progressively over the course of the study.

The total duration of the study is therefore estimated at 6 months.

2.2. Research hypotheses

The elderly frequently present stiffness in the various joints of the pelvic girdle. These limitations in pelvic amplitude, caused by muscular or rheumatic pathologies, induce a reduction in proprioceptive response, leading to increased gait or balance disorders, and possibly a fear of falling.

Is the intensity of joint stiffness associated with a heightened fear of falling in elderly patients?

2.3. JUSTIFICATION OF METHODOLOGICAL CHOICES

In our study, we aim to assess whether there is an association between joint stiffness (uncontrollable exposure) and fear of falling (uncontrollable event). The appropriate study design is therefore that of a prospective cohort with secondary analysis of subgroups within the cohort.

The FES-I is a reference test in geriatrics for assessing fear of falling. Its validity is recognized in geriatrics and for patients with minor cognitive impairment.

Goniometry and the Schober index provide a reliable assessment of joint mobility, with no lack of specificity or sensitivity compared with other joint mobility tests.

To measure the association between fear of falling and joint stiffness, we decided to record them at an instant T (inclusion). These variables may fluctuate within a patient, but it is not the evolution of these parameters that we wish to evaluate, only the implication of one on the other.

2.4. BENEFIT/RISK RATIO

The benefits of this study:

- Identify people at risk of fear of falling
- Identify a new risk factor for fear of falling, in order to adapt prevention measures.

Risk

There are no risks involved in this study.

2.5. EXPECTED BENEFITS

Fear of falling is a major concern in elderly patients. The risk factors identified are social, psychological, linked to a history of falls or the use of medication. This fear restricts physical activity and reduces quality of life.

The pelvic girdle is central to our postural balance. Its suppleness guarantees the proper adaptation of our static and dynamic body schema.

Aging can lead to osteoarticular stiffness and connective tissue fibrosis, a reduction in range of motion and thus a loss of proprioceptive adaptation of the pelvic girdle. By identifying joint stiffness as a risk factor for fear of falling, we can treat this factor and influence the fear of falling. Elderly patients regain confidence, their fear of falling diminishes and they are encouraged to resume physical activity gradually and at their own pace.

3. RESEARCH OBJECTIVES

3.1. MAIN OBJECTIVE

To demonstrate a significant association between the Schober index (quantitative) and/or hip goniometry in flexion (quantitative) and/or hip goniometry in extension (quantitative) with the FES-I score (qualitative 2 groups).

3.2. SECONDARY OBJECTIVES

- Validity of 3 FES-I categories according to anthropometric measurements
- Assessment of linearity of association
- Assessment of strength of association
- Impact of cofactors collected on FES-I (polypharmacy, history of falls).

4. EVALUATION CRITERIA

4.1. MAIN EVALUATION CRITERION

FES-I questionnaire

This questionnaire comprises sixteen items. It is an improved version of the Fall Efficacy Scale (FES) proposed by Tinetti (18). The FES-I was developed by the Prevention of Falls Network Europe (ProFaNE). It is available on the ProFaNE website. A version of the FES-I scale has been translated into French. The questionnaire works as follows: for each proposition (16 in all), respondents are asked to rate their level of anxiety when imagining themselves carrying out the corresponding action. For each item, the respondent's level of concern is rated on a scale from 1 to 4, with the following correspondences:

- 1 not at all worried;
- 2 a little worried;
- 3 quite worried;
- 4 very worried.

The final score for this test is therefore between 16 and 64. The higher the score, the greater the fear of falling. The cut-point for this questionnaire, defining a high level of apprehension about falling, is set for scores greater than or equal to 28, according to research by (Delbaere et al, 2010)⁵

Hip goniometry

Hip goniometry: expressed in degrees, measures hip joint amplitude in active flexion and extension using a goniometer. The measurement is taken standing up. We evaluate one hip, the one that appears most mobile to the patient. With the goniometer at the level of the greater trochanter, we ask the patient to actively flex the hip, knee bent, checking that the lumbar vertebrae are not engaged. Same procedure on the same leg for straight-leg hip extension.

Modified Schober index

Modified Schober Index: This test is used to identify patients with ankylosing spondylitis (Macrae & Wright, 1969)⁶ and assesses lumbar joint mobility in flexion. Subsequent studies have shown the test to be reliable and reproducible (Koppenhaver *et al.*, 2011)⁷, (Malanga *et al.*, 2005)⁸.

- When the patient is standing, a first mark is made at the sacro-lumbar junction or between the posterior-superior iliac spines;
- a second mark is made 10 cm above the sacro-lumbar junction;
- a third mark is made 5 cm below the sacro-lumbar junction;
- a measuring tape is stretched between the three marks and the distance between the first and third marks is recorded, in neutral position and at maximum flexion of the lumbar spine;
- a deviation of less than 5 cm is considered pathological.

Measurements of mobility in extension and lateral flexion are also available, since ankylosing spondylitis limits mobility in all planes of motion. (Moll *et al.*, 1971)⁹. Sensitivity

0.25 to 0.30 Specificity 0.86 to 0.95 Intra-examiner ICC 0.87 (good correlation) Inter-examiner ICC 0.79 (moderate correlation).

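### Read by its own mark numbers, the Modified Schober instruction records a 5 cm span below the sacro-lumbar junction, not the lumbar mobility it is meant to measure

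*Combined protocol and SAP*

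**What the plan says.** Section 4.1 numbers and places three marks on the standing patient:

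- Mark 1: "a first mark is made at the sacro-lumbar junction or between the posterior-superior iliac spines".
- Mark 2: "a second mark is made 10 cm above the sacro-lumbar junction".
- Mark 3: "a third mark is made 5 cm below the sacro-lumbar junction".

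The reading itself is specified as follows: "the distance between the first and third marks is recorded, in neutral position and at maximum flexion of the lumbar spine". On how the tape is laid for this reading, the section says that "a measuring tape is stretched between the three marks". The limit given is that "a deviation of less than 5 cm is considered pathological".

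The same section says the test "assesses lumbar joint mobility in flexion". The abstract describes the step as "evaluation of lumbar articular mobility by the schober index", and the data list in section 12.1 also labels the variable as lumbar.

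The index is one of the three measures in the main objective (section 3.1). In section 9 it is one of the three measures compared by Mann-Whitney test between the two FES-I groups.

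**The concern.** The instruction names the marks by number, and the pair it names does not measure what the section says the test measures. An examiner who follows the numbers records a distance that starts at the junction and runs downwards. The 10 cm above the junction, where mark 2 was drawn, plays no part.

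There is a second, smaller difficulty. Mark 1 has two permitted positions, but marks 2 and 3 are located only from the junction. If mark 1 is put between the iliac spines, the text no longer fixes the distance from mark 1 to mark 3.

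At stake is the meaning of one of the three primary variables. Section 4.1 is the only place in the document that describes how the index is taken. Section 7.3 lists it as a research act and not as care, section 5.1 lists three sites, and section 12.1 has the investigator at each site collect the data. If all examiners follow the numbers, the variable is consistent but is not lumbar mobility. If some use the numbered pair and others the outer marks, two quantities with different baselines are pooled under one name. Sections 12.1 and 12.2 list only the index as a data item, so such a mixture might not show in the database.

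**Working it through.** **Inputs.** All are from section 4.1. Take the junction as 0 cm and upwards as positive: mark 1 = 0, mark 2 = +10, mark 3 = −5. The limit is a deviation of 5 cm. Deviation is taken to mean flexion distance minus neutral distance, which the text implies but does not define. The plan gives no neutral span, so there is no stated figure to reproduce.

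**Step 1: spans with mark 1 at the junction.** Neutral span = absolute difference of the two positions. Elongation needed to reach the limit = 5 / neutral span.

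| Pair | Neutral span | Part above the junction | Elongation for a 5 cm deviation |
|---|---|---|---|
| 1 and 3 (as written) | 0 − (−5) = 5 cm | 0 of 10 cm | 5/5 = 100% |
| 1 and 2 | 10 − 0 = 10 cm | 10 of 10 cm | 5/10 = 50% |
| 2 and 3 (outer marks) | 10 − (−5) = 15 cm | 10 of 10 cm | 5/15 = 33% |

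The written pair is 5/15 = one third of the outer span and includes nothing above the junction. To escape the pathological label, it would have to lengthen from 5 to 10 cm.

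**Step 2: mark 1 between the iliac spines.** The document gives no offset d between this landmark and the junction. Purely as an assumption, let d run from −2 to +2 cm (positive = above the junction).

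- Marks 1 and 3: 5 + d = 3 to 7 cm, which is 3/15 = 20% to 7/15 = 47% of the outer span.
- Part above the junction: max(d, 0) = 0 to 2 of the 10 cm.
- Elongation for 5 cm: 5/3 = 167% down to 5/7 = 71%.
- Marks 2 and 3: 15 cm for every d, because both are placed from the junction.

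The conclusion does not depend on the assumed offset. Over this range the written pair still misses most or all of the region above the junction.

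**Step 3: which pair was meant.** The tape is laid across all three marks, and only marks 2 and 3 enclose all three. Ordered from top to bottom, the marks run 2, 1, 3, so first and third along the tape would be the outer pair. The 5 cm limit is also hard to reconcile with a 5 cm baseline. These are inferences: no section renumbers the marks or names the outer pair.

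**Step 4: reach in the analysis (section 9).** Tests firmly planned on the three measures: 3 Mann-Whitney + 3 regression slopes + 3 Spearman = 9, of which the Schober index has 1 + 1 + 1 = 3. The conditional subgroup Mann-Whitney tests (2 × 3 = 6, of which 2 are Schober), the optional chi-2 test and the descriptive three-category analysis are not counted. The 5 cm limit enters no planned test. These counts show where the variable is used, not that any result is wrong.

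**The case against.** The best defence is that the context corrects the slip. The tape spans three marks, the literal reading leaves one mark without use and needs the span to double, and the measure is called lumbar throughout. A trained examiner would probably use the outer marks without noticing the wording. Section 12.5 requires staff to be qualified for their tasks, all three sites belong to one geriatrics centre, and the number of examiners is not stated. The observation notebook is not reproduced, and the text appears to be a translation, so the working wording may differ. On this view the point is editorial.

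Much of this stands as evidence of intent, and it is why the outer marks are described here as probably meant. It does not change the instruction, which numbers each mark and then names the wrong pair for its purpose. A general requirement for qualified staff does not say which marks to use, and a notebook that cannot be seen cannot be relied on to correct the protocol.

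It can also be argued that lumbar purpose alone would equally allow marks 1 and 2, which lie at and above the junction. That is fair. The case for marks 2 and 3 rests mainly on the three-mark tape, so the sponsor should confirm that pair when correcting the text.

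Three further points are accepted. The two-position recording is already in section 4.1. Fixing one landmark does not alter the 15 cm span and is a separate gain in reproducibility. The change may need more than a note to sites, as discussed under the fix.

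**Conclusion.** The concern holds. Followed by its mark numbers, with mark 1 at the junction, the only instruction in the document for one of three primary measures yields a 5 cm span wholly below the sacro-lumbar junction. The likely intended span is 15 cm and runs across all three marks. The written pair fits neither the stated lumbar purpose nor the section's own 5 cm limit. With the alternative landmark, its length is not determined by the text.

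The arithmetic rests only on the mark positions in section 4.1, except for the ±2 cm offset, which is an assumption and does not drive the conclusion. That the outer marks were meant is a probable inference, not a stated fact.

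The consequence is limited. The document does not show what examiners did, so no damage to data, bias or loss of power is claimed. The two hip measures are unaffected, and the main objective is worded so that an association with any one of the three measures would meet it. The instruction should still be corrected, because it defines a primary variable and the correction is simple.

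**What to change.** Replace the recording sentence in section 4.1 with one that names the marks by position. For example: measure from the second mark (10 cm above the reference point) to the third mark (5 cm below it), nominally 15 cm in neutral, once in neutral and once at maximum lumbar flexion; the Schober index is the flexion distance minus the neutral distance.

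Choose one landmark for mark 1, use it at all sites, and place both other marks from it.

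Keep both distances, not only the index, as data items in the notebook and database. A neutral value near 5 cm instead of 15 cm would then reveal the wrong pair.

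Inclusion was scheduled from September 2021 (section 8.1), so data may already exist. If so, ask each examiner which marks were used before the index is analysed as lumbar mobility. Values taken between marks 1 and 3 should not be pooled with values from the outer marks.

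The cost is one corrected sentence, a note to three sites and, if data exist, one question per examiner. Tape, marks and visit stay the same. The sponsor should decide whether the change counts as substantial under section 13.2; if it does, a written amendment and a favourable ethics committee opinion add to the cost.
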